## B. Statistical Considerations

**Sample Size Justification:** We estimate there will be a small prevalence of occult infection among patients who are believed to be eligible after initial screening is completed. Patients with identified infection at the time of enrollment will not be randomized and instead be treated as per standard of care at the discretion of the medical staff. We estimate there may be 5-10 such patients who are thus enrolled but not randomized.

We aim to randomize a total of 40 subjects, assigned to active intervention vs. placebo; hence as many as 50 may be screened / consented to determine eligibility. This is a pilot study intended to assess feasibility of patient identification, administration of required testing and enrollment processing, and the rate thereof. The magnitude of observed effect will permit sample size estimation for a larger, more definitive study which we hope to complete subsequently. It is unknown how many subjects will need to be screened to complete this planned enrollment. We will also obtain information on the dropout rate and/or rate of use of therapeutic antibiotics which may alter enrollment goals for a future study.

**Data Analysis:** As stated elsewhere, the proposed study is a pilot study, not intended to provide definitive results. However, there are multiple outcomes of interest that will be recorded in order to permit planning of a future study.

The primary outcome is incident bacterial infection identified after randomization

screening (as defined below).

Secondary outcomes include:

1. In-hospital mortality;
2. 30-day mortality;
3. Incident acute on chronic liver failure (ACLF) defined as two or more of:
  - Grade 3-4 hepatic encephalopathy,
  - Need for renal replacement therapy,
  - Need for mechanical ventilation,
  - Need for vasopressors, or mean arterial pressure (MAP) <60 mmHg, or decrement of >40 mmHg in systolic blood pressure after volume resuscitation.
4. Change in calculated CLIF-C ACLF score;
5. Length of stay (LOS) after randomization;
6. Intensive Care Unit (ICU) transfer after randomization;
7. C difficile infection (positive stool polymerase chain reaction (PCR) or toxin-assay in the setting of diarrhea);
8. Increment in MELD-Na  $\geq 3$  points between randomization and discharge;
9. Acute kidney injury (increase in creatinine  $\geq 0.3$  mg/dL in 48 hr or  $>50\%$  from baseline (within previous 3 months) occurring after randomization;
10. Variceal hemorrhage.

Covariates recorded/measured

- Procalcitonin at enrollment
- C-reactive protein at enrollment
- Other antibiotic use in-hospital (type and duration)
- Fungal infections (by positive culture) or use of systemic anti-fungal medications.

We will monitor daily for the incidence of the outcomes above via review of the medical record and discussions with the inpatient providers (when necessary). For any subject with a positive culture result, the site, organism, and antibiotic susceptibility will be recorded when available.

Infection definitions

- Bacteremia (positive blood culture not felt to be a skin flora contaminant)
- Spontaneous bacterial peritonitis (ascites PMN count  $>250/\mu\text{L}$  or positive ascites culture in the setting of new abdominal pain, or unexplained leukocytosis, fever, hypotension, fever, acute kidney injury, or exacerbation of hepatic encephalopathy, i.e., increase in West Have grade)
- Pneumonia: Pulmonary infiltrate on chest x-ray (CXR) or computed tomography (CT) in the presence of A) respiratory symptom(s) (cough, pleuritic pain, or dyspnea) or B) auscultation findings, abnormal body temperature ( $>38\text{C}$  or  $<36\text{C}$ ), or newly abnormal leukocyte count  $>10,000/\text{microL}$  or  $<4,000/\text{microL}$  (if baseline leukocyte count  $>4,500/\text{microL}$ ).
- Skin or Soft Tissue Infection (SSTI): Superficial erythema, warmth, or fluctuance in the

skin/soft tissues felt to be secondary to infection by the inpatient team, excluding mild superficial thrombophlebitis from IV catheter insertion

- UTI: Urine leukocytes  $> 10/\text{hpf}$ , bacteruria, positive urine culture, urinary leukocyte esterase or nitrite in the presence of symptoms/signs of infection (dysuria, unexplained increased urinary frequency, fever, or leukocytosis)
- Other infections as identified by the primary medical team

For purposes of analysis, deidentified subject clinical data documenting the metrics above will be stored in a password protected file within the BIDMC network. Analysis will be conducted at BIDMC using R-studio software. There are no additional statistical consultants currently affiliated with this study. Descriptive statistics will include the incidence of the primary and secondary categorical outcomes in each arm with comparison via Chi-square test or Fisher's exact test for rare events. As noted elsewhere, we do not anticipate this study will provide sufficient statistical power to demonstrate statistically significant differences between groups, but we will need to have an idea of the magnitude of effect prior to planning such a study and hope to obtain this information here.

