### B2. SIGNIFICANCE AND BACKGROUND FOR THE STUDY

Advanced chronic liver disease/cirrhosis creates a state of relative immune-compromise, and, indeed, infections are a key precipitant of clinical decline in patients with cirrhosis. Specifically, infections of any kind are a common cause of acute on chronic liver failure (ACLF) and complicate 20-40% of hospital admissions of patients with cirrhosis. Although other pathogens are also important, the vast majority of infections in patients with cirrhosis are of bacterial origin. In other high-risk hospitalized patient populations, early initiation of antibiotics has been shown to reduce the need for intensive care unit (ICU) admission and short-term mortality. Unfortunately, the presentation of infection in patients with cirrhosis is protean and may be subtle. Diagnosis may be delayed by the absence of classic signs of infection such as fever and absolute leukocytosis. Vital diagnostic studies, such as paracentesis or other culture (blood, urine, or sputum) may be delayed or may not yield results until days after presentation. Delaying antibiotics until such studies result is inadvisable in patients with infection; however, empiric administration of antibiotics to all patients with cirrhosis admitted to the hospital would result in waste and increased risk of antibiotic resistance, *Clostridium difficile* infection, and other adverse effects. Sub-groups of patients with cirrhosis are already known to benefit from empiric/prophylactic antibiotics including those with acute upper gastrointestinal hemorrhage and those with increased risk of spontaneous bacterial peritonitis. The risk of infection increases with more advanced cirrhosis, as marked by higher Model for End-stage Liver Disease – Sodium (MELD-Na).

There are also biomarkers of systemic infection that, although not specific, may be used to identify patients more likely to have an active infection and thus allow more targeted use of empiric antibiotics. Specifically, increase in serum C-reactive protein (CRP, >25 mg/L) and Procalcitonin (>0.5 ng/mL) are associated with acute bacterial infection.

These factors may permit identification of patients who would benefit from prophylactic/empiric antibiotics. There has not, however, been investigation of the effect of prophylactic antibiotics on hospitalized patients with advanced cirrhosis beyond the sub-populations described above.

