**B3. DESCRIPTION OF RESEARCH PROTOCOL****A. Study Design – Overview, Methods, Procedures**

This is a blinded, randomized, placebo-controlled pilot trial to determine feasibility of subject identification, rate of enrollment, and data collection, including specimen processing, for a future, larger randomized trial of the effect of empiric antibiotics for all patients with advanced cirrhosis admitted to the hospital without an existing indication for new antibiotic use. Specifically, we will assess the incidence of infection after the time of enrollment and associated outcomes. Patients will be randomized to receive either ceftriaxone or placebo (normal saline). Study drug will be delivered in masked vials for daily IV administration.

**Case finding and Screening:** Eligible patients will be identified in the emergency department or by admitting physicians upon their initial medical assessment or by study personnel via daily review of the inpatient hepatology ward and consultative service census. Study personnel will screen each potential subject by review of medical record for potential eligibility.

**Consent:** If a patient meets basic eligibility criteria, a study investigator will meet with the potential subject/LAR to review the study protocol and obtain informed consent. Screening measures will be completed following consent and the balance of the baseline measures will be completed.

**Extended Screening/Baseline:** Evaluation for undiagnosed infection will be completed following consent and prior to randomization including: chest x-ray, venous blood culture, urine culture- all, if not already performed via routine care. These studies may be deferred if they have been done within 7 days of enrollment and there has been no change in clinical status. Subjects with infection identified upon enrollment will be excluded from further participation and have further treatment directed by their standard clinical providers.

Each subject's medical record will be reviewed to determine the presence or absence of diuretic-resistant ascites (defined by history of TIPS, large volume paracentesis within the past 3 months despite diuretics, or intolerance of diuretics).

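### The plan says the effect seen in 40 patients will permit sizing of the definitive trial, but one infection more or fewer can change the implied size about 1.5- to 4.6-fold, and no confidence interval is planned

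*Combined protocol and SAP*

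**What the plan says.** Section B, Statistical Considerations, sets the size of the pilot: "We aim to randomize a total of 40 subjects, assigned to active intervention vs. placebo". The number is justified by feasibility, with no error rate, power, effect or precision target behind it. The same paragraph then says of the next trial: "The magnitude of observed effect will permit sample size estimation for a larger, more definitive study which we hope to complete subsequently". It adds other planning inputs: "We will also obtain information on the dropout rate and/or rate of use of therapeutic antibiotics".

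Under Data Analysis in the same section, the plan says the pilot is not meant to give definitive results. The planned statistics are the "incidence of the primary and secondary categorical outcomes in each arm with comparison via Chi-square test", or Fisher's exact test when events are rare. The plan expects too little power for statistical significance, but explains that "we will need to have an idea of the magnitude of effect prior to planning such a study". No section plans a confidence interval for the between-arm difference or for any single rate. No section says how the observed effect would enter the later calculation.

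**The concern.** A sample size for two proportions varies with the inverse square of the difference between them. With about 20 patients per arm and a handful of infections, that difference is a matter of a few events, so an implied size taken from it is unstable. The admission of low power does not cover this, because it concerns significance and not the precision of the effect that is to be carried forward. An interval would show the reader how wide the range of compatible effects is, and none is planned.

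At stake is the planning of the definitive trial. A lucky pilot could lead to one that is too small. An unlucky pilot could suggest that there is nothing to pursue. The pilot's patients, conduct and tests are not affected.

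**Working it through.** **The plan's own figure.** No formula can reproduce 40, because none of its inputs is stated. The one sum that can be checked does agree: 40 randomised plus up to 10 enrolled but not randomised gives 50 ("hence as many as 50 may be screened / consented to determine eligibility").

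**Inputs.**
- From the plan: 40 randomised, two arms, and a binary primary outcome (incident bacterial infection after randomisation).
- Assumed: 1:1 allocation (20 per arm), a halving of risk, two-sided 5%, 80% power, and observed rates entered directly.
- Control rate assumed at 20%, 30% and 40%. The only figure in the documents is in B2, where infections "complicate 20-40% of hospital admissions of patients with cirrhosis". That describes cirrhosis admissions in general. The rate after randomisation may be lower, since "Subjects with infection identified upon enrollment will be excluded from further participation" (B3.A, Extended Screening/Baseline).

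**Step 1: implied size per arm.** n = (1.96 + 0.842)² × [p₁(1−p₁) + p₂(1−p₂)] / (p₁−p₂)², rounded up; the squared term is 7.85.
- 4/20 v 2/20: 7.85 × (0.16 + 0.09) / 0.10² = 196.2, so 197
- 6/20 v 3/20: 7.85 × (0.21 + 0.1275) / 0.15² = 117.8, so 118
- 8/20 v 4/20: 7.85 × (0.24 + 0.16) / 0.20² = 78.5, so 79

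**Step 2: move one infection in one arm.**

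| Observed | n per arm | After one event moved | Fold change |
|---|---|---|---|
| 4 v 2 | 197 | 4v1 73; 5v2 97; 3v2 683; 4v3 903 | 2.0 to 4.6 |
| 6 v 3 | 118 | 6v2 59; 7v3 70; 5v3 248; 6v4 291 | 1.7 to 2.5 |
| 8 v 4 | 79 | 8v3 47; 9v4 52; 7v4 136; 8v5 150 | 1.5 to 1.9 |

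A pooled-variance formula gives 199, 121 and 82 per arm, with largest changes of 4.6-, 2.4- and 1.85-fold, so the choice of formula does not drive the result.

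**Step 3: the interval the pilot could report.** The Newcombe 95% interval combines the two Wilson intervals. For 4 v 2 these are 0.081 to 0.416 and 0.028 to 0.301.
- Lower limit: 0.10 − √[(0.200−0.081)² + (0.301−0.100)²] = −0.134
- Upper limit: 0.10 + √[(0.416−0.200)² + (0.100−0.028)²] = 0.328

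In percentage points of risk reduction, the intervals are −13 to 33 (4 v 2), −11 to 39 (6 v 3) and −8 to 44 (8 v 4). All include zero.

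**Step 4: all possible pilots.** Every pair of counts from 0 to 20 was enumerated with exact binomial probabilities under a true halving. A favourable pilot is one with fewer infections on ceftriaxone. True power at a given n is Φ(|p₁−p₂| / √{[p₁(1−p₁) + p₂(1−p₂)]/n} − 1.96). At a 20% control rate and the median implied n of 97, that is Φ(0.10/√(0.25/97) − 1.96) = Φ(0.01), or 50%.

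| Control rate | 20% | 30% | 40% |
|---|---|---|---|
| Correct n per arm | 197 | 118 | 79 |
| Pilot tied or reversed | 25% | 17% | 11% |
| Favourable pilots: median implied n | 97 | 79 | 59 |
| Favourable pilots: implied n too small | 65% | 58% | 55% |
| Favourable pilots: median true power | 50% | 63% | 68% |

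**Step 5: sensitivity.** If the true reduction were 70% instead of 50%, median true power after a favourable pilot would be about 72%, 76% and 78%, close to the 80% target. In the other direction, a halving from a 10% control rate gives ties or reversals in 39% of pilots and a median true power of 35%.

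**The case against.** The strongest reply is that this is a feasibility pilot and largely says so. Data Analysis disclaims definitive results and speaks only of an idea of the effect, and B4 repeats that the pilot is not meant to confirm benefit. That stands: taken as a whole, the document treats the effect as a rough planning input, and one sentence is too strong. A reader might infer that the claim is made without qualification; the document does not support that.

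It can also be said that harm arises only if raw observed rates are put straight into a formula. The plan does not say it will do this, and it names dropout and antibiotic use as further inputs. This stands too: direct entry is an assumption here, although no other method is given.

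A reader might infer that the pilot will more often than not produce a trial that is too small. Under a halving, that holds only among favourable pilots; over all pilots the share is about 49%. A reader might also take two-fold as the least change from one event, but 5 of the 12 moves above are below two-fold.

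Finally, the list of descriptive statistics is open-ended, and anyone given counts and denominators can compute an interval. That lessens the omission but does not remove it, since the effect estimate is meant for planning and its precision should be reported with it.

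**Conclusion.** The concern holds, as a minor point. The sentence promises more than 40 patients can deliver, and the planned analysis omits the statistic that would show this. Under the stated assumptions (20 per arm, a halving of risk, control rates of 20% to 40%, direct entry of observed rates, two-sided 5% and 80% power), one infection changes the implied size about 1.5- to 4.6-fold. The instability is greatest when infections are few and shrinks as the observed difference grows. The shortfall in power depends on the assumed effect and is small if the true reduction is 70%.

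A reader might infer that the pilot itself is wrongly sized or its tests invalid. The documents do not support that: its feasibility aim does not rest on the effect estimate, and the consequence is confined to planning the next trial.

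**What to change.** 1. In Sample Size Justification, replace the claim that the observed effect will permit sizing with, for example: *The observed between-arm effect will be reported with its 95% confidence interval. It will inform planning of a definitive study but will not on its own determine its size.* This leaves the method for the later trial to that trial's protocol.
2. In Data Analysis, alongside the planned tests, add the between-arm risk difference for the primary outcome with a 95% interval (Newcombe, for example). Add 95% intervals for the placebo-arm infection rate, dropout and therapeutic antibiotic use. The placebo arm should be named, because a pooled rate would mix in any treatment effect.

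The cost is a few lines of analysis and a less favourable stated claim; no further patients or data are needed. The change does not remove the underlying uncertainty. A placebo rate of 4/20 has a Wilson 95% interval of 8% to 42%, and detecting a halving at those limits needs 545 and 74 per arm respectively, about a seven-fold range. The intervals make that visible to whoever plans the next trial.

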**Monitoring during Study Intervention:** Monitoring during study treatment will utilize routine vital sign monitoring and standard care labs conducted as indicated (typically daily) during the patient's in patient stay. Standard care monitoring may also include radiographic or microbiology studies (e.g. culture) or special procedures such as therapeutic or diagnostic paracentesis at the discretion of the inpatient care team. No additional monitoring will be required per the study protocol. Standard care monitoring/labs that will be of interests include vital signs (e.g. blood pressure, mean arterial pressure, and oxygen saturation), CBC with WBC differential, bilirubin, INR, serum creatinine, sodium, albumin.

**Incidental Findings:** In the event that a clinically significant incidental finding is discovered during a research procedure, findings will be immediately reported to the attending on service for treatment or referral; results will be in OMR. These would be also be available to the in-patients care team via OMR. Examples of incidental findings include previously un-identified lung findings on chest x-ray, such as infection, pulmonary nodule, fracture, etc.

**Safety Monitoring:** The PI is ultimately responsible for protecting the rights, safety, and welfare of subjects enrolled into the trial. Study intervention will last for 7 days during the patient's inpatient stay for conditions related to the diagnosis of advanced cirrhosis/end stage liver disease. Safety monitoring will be conducted daily during the intervention phase; post-intervention procedures will continue daily during the patient's admission and on day 30 post end of intervention. The PI and/or a co-physician investigator will review all safety parameters including clinical safety laboratory assessments. Clinical laboratory values that fall outside of the pre-specified safety ranges will be brought to the PIs attention the day the reports are final to assess clinical significance.

Patients in the trial will be under the care of the in-patient liver service and these medical staff will be responsible for care of the patient throughout the admission.

The study PI will review data of all non-serious adverse events after randomization of the first 5 subjects, and every additional 10 subjects thereafter until the study is complete.

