#### ***Inclusion Criteria:***

- Age  $\geq 18$
- Cirrhosis, as defined by liver biopsy (completed as standard care) or a composite assessment of available results from imaging or elastography, prior records, and laboratory studies
- MELD-Na  $\geq 18$  (Model for End Stage Liver Disease-Sodium, incorporating components of serum sodium, bilirubin, International Normalized Ratio (INR), and creatinine

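### Secondary outcome 8 records MELD-Na change only as a yes/no rise of at least 3 points, so the pilot yields no mean difference or SD of that change; a continuous analysis should be added beside it

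*Combined protocol and SAP*

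**What the plan says.** Item 8 of the secondary outcomes (B. Statistical Considerations, Data Analysis) is a MELD-Na increase of at least 3 "points between randomization and discharge". No other MELD-Na outcome is listed. The analysis paragraph covers the "incidence of the primary and secondary categorical outcomes in each arm with comparison via Chi-square test or Fisher's exact test for rare events". It names no method for any continuous outcome, although item 4 (change in CLIF-C ACLF score, no cut-off) and item 5 (length of stay) are continuous.

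MELD-Na is computed at entry, because the inclusion criteria require a value of at least 18, "incorporating components of serum sodium, bilirubin, International Normalized Ratio (INR), and creatinine". During treatment, the standard-care labs of interest include "bilirubin, INR, serum creatinine, sodium, albumin", which covers all four components. B3.A describes these labs as drawn when indicated, typically daily. It adds no study-required monitoring, so there is no mandated discharge sample.

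On size and purpose: "We aim to randomize a total of 40 subjects, assigned to active intervention vs. placebo". The allocation ratio is not given. The same section says that the study is not expected to have adequate power, and that the observed effect sizes are meant to inform the sample size of a larger trial.

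**The concern.** Scoring item 8 for a patient requires two MELD-Na values, and the yes/no form keeps only whether their difference reaches 3. A patient who improves by 8 points scores the same as one who worsens by 2. The documents give no reason for the cut-off, while the comparable CLIF-C ACLF score is kept as a change.

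What is at stake is planning rather than a significance test. Two percentages from about 20 patients each do not supply a mean difference, an SD of change or a relation to baseline. Those are the quantities needed to size a later trial on the score itself.

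**Working it through.** The plan has no figure to reproduce: 40 is a feasibility number, and item 8 has no SD, event share, effect size, alpha or power behind it.

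**Inputs from the documents:** 40 randomized; cut-off of 3 points; Chi-square, or Fisher for rare events.

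**Assumed inputs:** 1:1 allocation (20 per arm), two-sided alpha 0.05, 80% power where a sample size is shown, and normally distributed change with the same shift in every patient.

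**1. Information kept by the yes/no form.** For a small shift, relative efficiency is φ(c)² / [p(1−p)], where p is the share of patients rising by at least 3 points and c is the matching normal quantile.

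| p | c | φ(c) | Efficiency | Loss |
|---|---|---|---|---|
| 10% | 1.282 | 0.1755 | 0.0308/0.09 = 0.342 | 66% |
| 20% | 0.842 | 0.2800 | 0.0784/0.16 = 0.490 | 51% |
| 50% | 0 | 0.3989 | 0.1592/0.25 = 0.637 | 36% |

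At p = 20%, 40 patients scored yes/no carry the information of 40 × 0.490 = 19.6 analysed as a continuous change. At 10% the figure is 13.7, and at 50% it is 25.5.

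**2. A finite shift.** Take SD 5, control mean change 0 and a shift of 2.5 points. On the integer scale a rise of at least 3 is taken as a value above 2.5.

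- Control share: 1 − Φ(2.5/5) = 30.9%. Treated share: 1 − Φ(5/5) = 15.9%.
- Continuous: 2(1.960 + 0.842)² / (2.5/5)² = 15.70/0.25 = 62.8, so 63 per arm.
- Yes/no, pooled two-proportion formula: 123.9, so 124 per arm. Ratio 123.9/62.8 = 1.97.
- Over SD 4 to 7 and control mean −1 to +1, the ratio runs from 1.67 (SD 7, mean +1) to 2.82 (SD 4, mean −1).

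**3. Power at 20 per arm** (control mean 0, shift 2.5; exact enumeration for the yes/no tests, noncentral t for the t-test):

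| SD | Fisher | Chi-square, uncorrected | t-test |
|---|---|---|---|
| 4 | 16% | 26% | 49% |
| 5 | 12% | 20% | 34% |
| 7 | 8% | 14% | 20% |

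At SD 5 the gap to the t-test is 22 percentage points with Fisher and 14 with Chi-square. The difference of 8 points comes from Fisher's conservatism, not from dichotomising.

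**4. A different effect pattern.** Suppose treatment prevents 60% of rises of at least 3 points and changes nothing else (assumed mean −1, SD 4, simulated with integer scores; prevented rises are reset to 0, 1 or 2). Power at 20 per arm is then 18% for Chi-square against 7% for the t-test. At 100 per arm it is 67% against 12%. The ordering reverses.

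**The case against.** The strongest case for leaving the plan alone has four parts.

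- **Mechanism.** The drug is meant to prevent infection, and B2 describes infection as a precipitant of clinical decline. An effect confined to large deteriorations is plausible, and step 4 shows that the threshold then does better. This stands, and it is why item 8 should be kept.
- **Aims.** The study disclaims power, this is the eighth of ten secondary outcomes, and nothing says that a later trial would be sized on continuous MELD-Na. This limits the weight of the point. It does not remove it, because the outcomes are collected to inform planning and the threshold result serves that use only if the same cut-off is used again.
- **Nothing is lost.** The analysis paragraph says what the descriptive statistics will include, which is not an exclusive list, and the clinical data are stored. A reader might infer that the plan discards the MELD-Na values. The documents do not support that: a mean and SD could be computed later. The gap is that no such analysis is specified.
- **Undefined values.** MELD-Na at discharge does not exist for a patient who dies in hospital and is not comparable after transplantation, so a plain regression would quietly be limited to survivors. This stands against replacing item 8 and must be met by any added analysis. Item 8 itself is equally silent on how such patients are scored.

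**Conclusion.** The point holds in a limited form. Item 8 does not count improvement, and as specified it gives no mean difference or SD of MELD-Na change, although scoring it uses both values.

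The size is conditional. Under an equal shift in a normally distributed change, the loss is about 36% to 66% for event shares of 50% down to 10%. In the worked case (20 per arm, SD 5, control mean 0, shift 2.5), power is about 20% by Chi-square or 12% by Fisher, against 34% by t-test.

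A reader might infer that the cut-off simply costs half the sample. The documents give no SD, event share or effect size to support that as a fact. About half is the value near a 20% event share under this one model, and the ordering reverses if only large rises are prevented. Nor do the documents support dropping the threshold, which is a legitimate measure of deterioration. Improvement is also not ignored study-wide, since item 4 keeps CLIF-C ACLF as a change.

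**What to change.** Keep item 8 and its comparison by arm. Add to the secondary outcomes and to the analysis paragraph of B. Statistical Considerations:

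- A continuous analysis of discharge MELD-Na, defined as the last available in-hospital value, by linear regression on arm with randomization MELD-Na as covariate. Report the adjusted mean difference with its confidence interval, and the residual SD.
- In-hospital deaths and transplants counted by arm. For transplanted patients, use the last value before transplantation.
- A rank-based sensitivity analysis that places in-hospital deaths as worst.

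**Cost:** one or two more analyses and a stated rule for deaths, transplants and the choice of last value. The components are already taken from routine care, so no new samples or visits are needed. The gain is modest and depends on how the drug acts.
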